#### 11.4 Data Analyses Plans

The primary endpoint is the progression-free survival proportion measured after 4 months of study treatment for patients in the IIT population. This endpoint is defined as the proportion of evaluable patients alive and progression-free after 4 months of study treatment in the event of no loss to follow-up and/or early patient discontinuation. The outcome is expected to be observed for each patient. In the event that either loss to follow-up or early discontinuation occurs (either not secondary to toxicity), the 4-month PFS will be estimated using the product-limit method of Kaplan and Meier. Follow-up time will be defined as time from the date of first study treatment (PFS1) and 1st line platinum-based therapy (PFS2) until the date of radiological (as per combined RECIST v1.1 and irRECIST criteria) or clinical progression (leading to withdrawal from the study treatment), or loss to follow-up due to toxicity or non-compliance with study procedures, or death from any cause, whichever comes first. Follow-up time will be censored at the date of last disease evaluation. Estimates for the median and 75th percentiles with 95% confidence intervals will be reported. In order to adjust for the patient's exposure to primary platinum-based therapy, a secondary analysis will utilize the Cox proportional hazards model with exposure time entered as an adjustment covariate as either a continuous covariate or as 4 months of exposure versus more than 4 months of exposure. OS will be similarly estimated and summarized with follow-up time calculated from the date of first study treatment (OS1) and 1st line platinum-based therapy (OS2) until date of death or censoring. ORR will be determined as per the irRECIST guidelines for the IIT population. Other safety data (e.g., laboratory safety parameters, vital signs, and new physical examination findings) will be summarized descriptively for the IIT population by reporting counts and percentages, with exact binomial confidence intervals where appropriate. Adverse events will be reported per the NCI Common Toxicity Criteria for Adverse Events (CTCAE) version 5.0.

#### 11.5 Early Stopping Rules Due to Toxicity

In order to protect patients from potential undue severe toxicity of this regimen, we have implemented stopping rules for documented SAE events that are at least possibly attributable to the study regimen. Using data from study of rucaparib monotherapy as maintenance therapy in ovarian cancer (phase 3 ARIEL3 trial; Coleman RL et al. Lancet. 2017 Oct 28;390(10106):1949-1961) as a guide, which had a SAE rate of 21% - defined as the percentage of patients experiencing at least one SAE during study treatment. In addition, the investigation of nivolumab in hepatocellular carcinoma (CHECKMATE-040 trial; El-Khoueiry AB et al. Lancet. 2017 Jun 24;389(10088):2492-2502) had a SAE rate of 4%. During the conduct of this proposed study, if we become confident from accumulating study data that the SAE rate, defined in the same way, involves more than 30% patients, then we will halt accrual on the trial in order to convene the data safety monitoring board (DSMB). The DSMB will review types and outcome of toxicity events and to recommend study closure or changes that could improve the trial.

To operationalize this stopping rule we have used a Bayesian sequential stopping rule under the beta-binomial relationship between prior expectation of toxicity and accumulating toxicity data. We have used a pessimistic and slightly informative prior, the uniform, to suggest that prior to study data we believe the percentage of SAE is equally like between 0 and 100%, with an average of 50%. If the posterior probability after study data is 80% or greater that the SAE probability per patient is 30% or greater, we will halt the trial. The following table lists the number of patients accrued and the number of patients experiencing an SAE to trigger stopping the trial. The rule is implemented after 5 patients are accrued.

| Number of patients on study treatment | Number experiencing SAE |
|---------------------------------------|-------------------------|
| 1 – 5                                 | No rule to apply –      |

|         | too early |
|---------|-----------|
| 6 – 10  | 6         |
| 11 – 12 | 7         |
| 13 – 14 | 8         |
| 15 – 16 | 9         |
| 17 – 18 | 10        |
| 19 – 20 | 11        |
| 20 – 22 | 12        |
| 23 – 24 | 13        |
| 25 – 26 | 14        |
| 27 – 28 | 15        |
| 29 – 30 | 16        |
| 31 – 32 | 17        |

Under this rule, if the true probability of SAE was 20%, 30%, 40%, 50%, or 60% the trial would stop early <1%, 8%, 30%, 62%, and 71%, respectively. And the expected sample size for the trial would be 32, 31, 27, 21, and 19 patients, respectively.

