#### 8.2.2 Serious Adverse Event

An adverse event is considered "serious" if, in the view of either the investigator or sponsor investigator, it results in any of the following outcomes:

- Death
   If death results from (progression of) the disease, the disease should be reported as event (SAE) itself.
- A life-threatening adverse event
   An adverse even is considered 'life-threatening' if, in the view of either the
   investigator [or sponsor investigator], its occurrence places the patient or
   subject at immediate risk of death. It does not include an adverse event that,
   had it occurred in a more severe form, might have caused death.
- Inpatient hospitalization or prolongation of existing hospitalization for ≥ 24 hours
- A persistent or significant incapacity or substantial disruption of the ability to conduct normal life functions
- A congenital anomaly/birth defect
- O Important medical event
  Any event that may not result in death, be life-threatening, or require
  hospitalization may be considered serious when, based upon appropriate
  medical judgment, they may jeopardize the patient and may require medical
  or surgical intervention to prevent one of the outcomes listed in this definition
  of "Serious Adverse Event". Examples of such medical events include
  allergic bronchospasm requiring intensive treatment in an emergency room
  or at home; convulsions that do not result in inpatient hospitalization or the
  development of drug dependency or drug abuse.

Events or outcomes not qualifying as SAEs:

- Previously planned (prior to signing the informed consent form) surgeries should not be reported as SAEs unless the underlying medical condition has worsened during the course of the study.
- Preplanned hospitalizations or procedures for preexisting conditions that are already recorded in the patient's medical history at the time of study enrollment should not be considered SAEs.
- Hospitalization or prolongation of hospitalization without a precipitating clinical AE (for example, for the administration of study therapy or other protocol-required procedure) should not be considered SAEs. However, if the preexisting condition worsened during the course of the study, it should be reported as an SAE.

Events of progression of the patient's underlying cancer as well as
events clearly related to progression of the patient's cancer (signs and
symptoms of progression) should not be reported as an SAE unless the

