# 8.2.4 Adverse Events of Special Interest (AESI)

AESIs (serious or non-serious) are defined as AEs of scientific and medical concern specific to the sponsor's product or program, for which ongoing monitoring and rapid communication by the investigator to the sponsor can be appropriate. Such an event might warrant further investigation in order to characterize and understand it. Depending on the nature of the event, rapid communication by the trial sponsor to other parties (e.g., regulators) might also be warranted.

All AESIs must be reported as SAEs and will be collected throughout the subject's participation in the study.

The AESI(s) for this trial are:

- Myelodysplastic Syndrome and Acute Myeloid Leukemia
- Pneumonitis

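### Section 11.5 defines the event behind the toxicity stopping rule in two incompatible ways, so the same data can halt accrual or let it continue

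*Combined protocol and SAP*

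**What the plan says.** All the competing wording is in section 11.5.

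- **Scope.** The opening sentence says the rules are for "documented SAE events that are at least possibly attributable to the study regimen".
- **Guide rate.** The 21% from the rucaparib maintenance trial is "defined as the percentage of patients experiencing at least one SAE during study treatment". Attribution is not mentioned. The 4% from the nivolumab trial in hepatocellular carcinoma is given with no definition.
- **Limit.** Accrual halts if the investigators become confident that "the SAE rate, defined in the same way, involves more than 30% patients". The only rate definition in the text before this is the one attached to the 21%.
- **Trigger.** The prior is uniform. The trial halts when the posterior probability that the per-patient SAE probability is at least 30% reaches 80%.
- **Table and operating characteristics.** Both refer to SAE with no attribution qualifier.

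Section 8 makes both counts available. Under 8.4.1 all SAEs are reported whatever their cause, and under 8.3.2 attribution is graded separately. Section 8.2.2 counts fatal progression as an SAE: "If death results from (progression of) the disease, the disease should be reported as event (SAE) itself". Section 8.2.4 adds "All AESIs must be reported as SAEs", and it covers serious and non-serious events alike.

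**The concern.** A stopping boundary works only if the event counted is the event on which the limit was set. Here the scope sentence points to treatment-attributable SAEs, while the guide rate and the limit point to any SAE. Two people applying the rule in good faith could enter different numbers in the same table row.

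Section 8.8 refers to 11.5 for stopping, and no other numerical safety boundary appears in the protocol. Section 5.1 says the safety profile of the two agents was evaluated individually, so this rule is the formal check on the combination. Setting an attributable count against a limit guided by an any-SAE rate makes the rule less sensitive. Counting any SAE lets events unrelated to the regimen, fatal progression among them, contribute to a halt.

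**Working it through.** **Inputs (sections 11.2 and 11.5).** Maximum 32 patients; rule active from patient 6; uniform prior; limit 30%; posterior cut-off 80%; printed boundaries from 6 events at 6–10 patients to 17 at 31–32. The printed rows 19–20 and 20–22 overlap at 20 patients. I read the second as 21–22, so the boundary at 20 is 11.

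**Formulas.** With k of n patients having the event, the posterior is Beta(1 + k, 1 + n − k). For the stopping probability at a true rate p, the probability of k events among n patients without an earlier stop is f(n, k) = (1 − p)·f(n − 1, k) + p·f(n − 1, k − 1). Mass at or above the boundary is removed at each n from 6 to 32 and summed.

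**Step 1: the plan's own figures.** Ranges are without and with a crossing at patient 32.

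| True SAE rate | Stated stop | Recomputed stop | Stated expected N | Recomputed expected N |
|---|---|---|---|---|
| 20% | <1% | 0.8% | 32 | 31.8 |
| 30% | 8% | 7.4% | 31 | 30.5 |
| 40% | 30% | 29% | 27 | 26.4 |
| 50% | 62% | 65–66% | 21 | 19.5 |
| 60% | 71% | 91–92% | 19 | 13.0 |

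The first three stopping probabilities agree with the plan; the last two do not. The table also does not follow from the written rule. A uniform prior with an 80% cut-off at 30% gives boundaries of 3, 5, 8 and 12 at 6, 10, 20 and 32 patients, against 6, 6, 11 and 17 printed. That is a separate matter, but it makes the results in step 3 conditional on the printed table.

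**Step 2: one data set, two actions.** Take 20 patients, 11 with any SAE and 6 with an SAE at least possibly attributable.

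- Any SAE: 11 meets the boundary of 11. The posterior is Beta(12, 10), and the probability that the rate is at least 30% is 0.991. Accrual halts.
- Attributable SAE: 6 is below 11. The posterior is Beta(7, 15), and the probability is 0.551. Accrual continues.

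The written 80% rule (boundary 8 at 20 patients) gives the same split. So does the printed table at 19 patients, where the boundary is 11 and no rows overlap.

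**Step 3: size over a range.** The documents do not give the share of SAE patients who have an attributable SAE, so it is varied. Attributable rate = any-SAE rate × share; for example 40% × 0.50 = 20% and 40% × 0.75 = 30%. Probability of stopping by the printed table, with a crossing at patient 32 counted:

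| True any-SAE rate | Any-SAE count | Attributable, share 50% | Attributable, share 75% | Attributable, share 100% |
|---|---|---|---|---|
| 30% | 7.4% | 0.2% | 1.6% | 7.4% |
| 40% | 29% | 0.8% | 7.4% | 29% |
| 50% | 66% | 2.8% | 22% | 66% |
| 60% | 92% | 7.4% | 47% | 92% |

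By the written 80%/30% rule, at a true any-SAE rate of 40%, the any-SAE count stops with probability 86%. The attributable count stops with probability 20% at a 50% share and 55% at a 75% share. The conflict therefore does not depend on which boundary is used.

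**The case against.** The strongest reply is that the opening sentence governs the whole section. Later mentions of SAE would then be shorthand for attributable SAE, and the limit would borrow from the guide rate only its unit, patients with at least one event. That reading is possible, so the documents do not support a flat statement that the any-SAE definition is the operative one. It still leaves an attributable count judged against a limit guided by a rate that the plan defines without attribution, so the text needs correcting either way.

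A second reply is that a crossing only halts accrual so that the DSMB can review the types and outcomes of events, and that the DSMC receives quarterly reports (section 13). Both are true and soften an unnecessary halt. Neither defines the trigger, and the DSMB review begins only once it has been met.

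Several stronger inferences are tempting but unsupported:

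- That both guide rates are any-SAE rates. Only the 21% carries a definition.
- That the guide rates set the boundary. They are offered as a guide; the written rule uses only the prior, the 30% limit and the 80% cut-off.
- That one patient could count more than once. Section 11.5 already counts patients.
- That AESIs enter only under the any-SAE reading. One judged at least possibly related counts under both.
- That disease progression generally would fill the count. Section 8.2.2 keeps non-fatal progression and its symptoms out of SAE reporting, and the guide-rate definition is confined to the treatment period. Fatal progression does meet 8.2.2.

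**Conclusion.** The point holds as an internal contradiction in 11.5: the event for the stopping rule is defined in two ways, and the table does not say which applies. The contradiction and the 20-patient example need no assumed share; the example needs only the row reading given above, and the 19-patient case does not need even that.

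The size does rest on assumptions. At a true any-SAE rate of 40%, the printed table gives a 29% chance of stopping on any SAE, against 0.8% to 29% on attributable SAEs as the share runs from 50% to 100%. A reader might take the widest gap as the expected effect; the documents give no share that would support this. The calculation also assumes independent patients with a constant rate and is conditional on the printed table. The text should be corrected because it governs a safety decision.

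**What to change.** State the countable event once in 11.5 and use it for the count, the 30% limit, the boundary table and the operating characteristics. There are two consistent options:

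- **Attributable SAE.** Keep the attribution condition, remove the words that carry the guide rate's definition over to the limit, and either say that the 21% is an any-SAE rate or replace it with a sourced attributable rate.
- **Any SAE.** Delete the attribution condition from the opening sentence. State whether fatal progression counts, and whether AESIs count when they are reported as SAEs but are not serious by 8.2.2.

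Under either option, say what the 4% measures or that its definition is not known. The sponsor chooses the definition; the passages must be reconciled. The cost is one paragraph and no new trial data, though an attributable guide rate would need a published source outside these documents.

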# 5.2 Toxicities and Dosing Delays/Dose Modifications

Any patient who receives treatment on this protocol will be evaluable for toxicity. Each patient will be assessed for the development of toxicity according to the Time and Events Table (Section 6.2). Toxicity will be assessed according to the NCI Common Terminology Criteria for Adverse Events (CTCAE), version 5.0. Dose adjustments should be made according to the system showing the greatest degree of toxicity.

| Table 2. Dose Modifications |               |                        |               |  |  |  |  |
|-----------------------------|---------------|------------------------|---------------|--|--|--|--|
| Drug                        | Current Dose  | Percentage
Decrease | Modified Dose |  |  |  |  |
|                             | 600 mg PO BID | ~20%                   | 500 mg PO BID |  |  |  |  |
| Pucaparib                   | 500 mg PO BID | 20%                    | 400 mg PO BID |  |  |  |  |
| Rucaparib                   | 400 mg PO BID | ~20%                   | 300 mg PO BID |  |  |  |  |
|                             | 300 mg PO BID | 100%                   | Discontinue   |  |  |  |  |
| Nivolumab                   | 240 mg IV     | 100%                   | Discontinue   |  |  |  |  |

- If more than one toxicity occurs requiring dose reduction, the dose administered should be based on the most severe toxicity.
- Treatment delay of more than 21 days from last intended therapy will result in discontinuation from trial, unless otherwise agreed and documented between the investigator and the sponsor.
- If one of the drugs is held or discontinued due to toxicity attributed to that agent, the patient will be allowed to continue the rest of the combination therapy.
- Nivolumab cannot be dose reduced and can only be discontinued as per detailed algorithms for immune-therapy toxicity management in Appendix III.

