# 5.10 Patient Replacement

All patients that receive at least one dose of study therapy will be considered evaluable for toxicity and will be considered a member of the intent-to-treat (IIT) population.

Patients enrolled on the study will be replaced and not considered a member of the IIT for the following reasons

- 1. Patients who did not receive even one dose of investigational therapy on study.
- 2. Patients that withdraw consent for study therapy prior to first response evaluation not secondary to toxicity.
- 3. Patients meeting off study criteria 5.9.1 and/or 5.9.3 not secondary to toxicity.
- 4. Patients meeting off study criteria 5.9.2 and/or 5.9.5

We expect the proportion of patients needed to be replaced to be extremely small for this clinical trial, at or less than 10% of those enrolled. Maximum enrollment to this trial will be increased to 35 patients if the necessity to replace patients is encountered.

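### Section 11.5 contains two different toxicity halting rules: the written 80%/30% criterion first triggers at 3/6 and 12/32, its table at 6/6 and 17/32, and the printed 71% matches neither

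*Combined protocol and SAP*

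**What the plan says.** Section 11.5 (Early Stopping Rules Due to Toxicity) opens with the aim: if the "SAE rate, defined in the same way, involves more than 30% patients, then we will halt accrual on the trial" so that the board can be convened. It then makes this operational with a beta-binomial model and a uniform prior. The criterion for halting reads: "posterior probability after study data is 80% or greater that the SAE probability per patient is 30% or greater, we will halt the trial". It applies once 5 patients have been accrued.

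The link to the table is explicit: "The following table lists the number of patients accrued and the number of patients experiencing an SAE to trigger stopping the trial". The table runs from 6 patients with an SAE at 6–10 on treatment to 17 at 31–32. Sample size 20 sits in two rows, 19–20 (trigger 11) and 20–22 (trigger 12).

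The section closes with operating characteristics at true SAE rates of 20, 30, 40, 50 and 60%. On halting it says "the trial would stop early <1%, 8%, 30%, 62%, and 71%, respectively". On average trial size, in the same order, it says "expected sample size for the trial would be 32, 31, 27, 21, and 19 patients".

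On who is counted, section 5.2 says "Any patient who receives treatment on this protocol will be evaluable for toxicity". Section 5.10 says "Patients enrolled on the study will be replaced and not considered a member of the IIT for the following reasons" and adds "Maximum enrollment to this trial will be increased to 35 patients if the necessity to replace patients is encountered". Section 11.3 makes that same intent-to-treat population the one used for safety.

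**The concern.** Prior, model, cut-off and limit are all stated, so the table can be recomputed. Its first entry already looks wrong. Under a uniform prior, 6 events in 6 patients puts the probability of a rate above 30% at almost 1, far beyond 80%.

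This is the plan's only quantitative trial-level toxicity trigger. If sentence and table differ, whoever applies section 11.5 cannot comply with both. A committee that approves the trial on the stated rationale would also expect much earlier halting than the table delivers. The printed operating characteristics should show which rule was meant, so they need checking too.

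**Working it through.** **Inputs, all from section 11.5 unless noted.** Prior Beta(1,1); halt if P(rate ≥ 0.30) ≥ 0.80; first look at n = 6; table triggers as printed, with n = 20 read as 11; maximum n = 32 (section 11.2). The look schedule is not stated. I assume a look after every patient and vary that below.

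**Step 1: boundary implied by the sentence.** After k of n patients with an SAE the posterior is Beta(1+k, 1+n−k). Its upper tail at 0.30 equals P(Bin(n+1, 0.30) ≤ k), which can be checked by hand; for 6/6 it is 1 − 0.3^7 = 0.9998.

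| n | last count below 80% | first count at 80% or more | table trigger | posterior at table trigger |
|---|---|---|---|---|
| 6 | 2 (0.647) | 3 (0.874) | 6 | 0.9998 |
| 10 | 4 (0.790) | 5 (0.922) | 6 | 0.978 |
| 20 | 7 (0.723) | 8 (0.852) | 11 (or 12) | 0.991 (at 11) |
| 32 | 11 (0.733) | 12 (0.839) | 17 | 0.997 |

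Over all 27 sample sizes from 6 to 32 the table exceeds the sentence, by 1 patient at n = 10 and by up to 5 (reached at n = 31–32, among others). Beta(0.5, 0.5) and Beta(2, 2) priors leave 3/6 and 12/32 unchanged, so the choice of prior does not explain the gap.

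**Step 2: could another cut-off on 30% give the table?** No. The table halts at 6/10 (posterior 0.978) but continues at 16/31 (0.995), so no single cut-off works. An 80% cut-off on a 45% limit reproduces the table at every n from 9 to 32, but not at 6–8, where it gives 4, 5 and 5. No 45% limit appears in section 11.5, and other combinations fit equally well.

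**Step 3: operating characteristics.** Let f_n(k) be the probability of k SAE patients among the first n without a halt so far, and b(n) the boundary. Then f_n(k) = (1−p)·f_{n−1}(k) + p·f_{n−1}(k−1). At each look the mass with k ≥ b(n) is moved to h_n, the probability of halting at n. P(halt) = Σh_n and E[N] = Σ n·h_n + 32·(1 − Σh_n).

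| True rate | Printed: halt, E[N] | Table: halt, E[N] | Sentence: halt, E[N] |
|---|---|---|---|
| 20% | <1%, 32 | 0.8%, 31.8 | 19.9%, 27.3 |
| 30% | 8%, 31 | 7.4%, 30.5 | 54.8%, 20.0 |
| 40% | 30%, 27 | 29.4%, 26.4 | 86.3%, 12.8 |
| 50% | 62%, 21 | 65.6%, 19.5 | 98.2%, 8.5 |
| 60% | 71%, 19 | 92.1%, 13.0 | 99.9%, 6.8 |

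The printed figures reproduce from the table at 20–40%. At 50% they are slightly low, which a sparser look schedule could explain. At 60% they fit neither rule. Reading n = 20 as 12 changes the table's halting figures by at most 0.3 points.

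**Step 4: can a look schedule rescue 71%?** P(X ≥ 17 | n = 32, p = 0.6) = 83.5%, and adding looks can only raise it. So 71% is impossible for any schedule that includes patient 32. Looks at row starts, row ends, or every 5, 6, 8 or 10 patients give 87–92% at a true 60%. A single look at n = 16 gives 71.6% at 60%, but only 14% at 40% and 40% at 50%, against a printed 30% and 62%. Truncating the patient-by-patient looks does not help. The table reaches 70.5% at a true 60% by n = 12, but a true 50% then gives only 43.8%.

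**Step 5: how often the rules disagree.** The table is above the sentence at every n, so its halts are a subset of the sentence's. The share of trials halted by the sentence but never by the table is the difference: 54.8 − 7.4 = 47.4% at a true 30%, and 86.3 − 29.4 = 56.9% at 40%. At 5/6, 5/10 and 16/32 the posteriors are 99.6%, 92.2% and 99.2%. The sentence says halt and the table says continue.

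**The case against.** The strongest reply is that the table is the working rule. It is introduced as the list of triggers, the printed 20–40% figures were evidently computed from it, and those figures openly show weak stopping (8% at a true 30%, 30% at 40%). On that reading the text misdescribes the rule and the 47% and 57% disagreement is hypothetical. A trigger also only pauses accrual for a board review. SAEs reach the Coordinating Center within 24 hours (section 8.4.1), and the committee reviews data quarterly (section 13).

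Much of this is fair and it limits the harm. It does not remove the contradiction: the sentence is written as a binding criterion, 30% is named twice as the limit, and the 71% is wrong for the table too.

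Three further limits stand:

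- The recomputed operating characteristics depend on the look schedule. With looks every 5 patients the table gives about 25/60/89% at 40/50/60%, rather than 29/66/92%.
- The counted event is itself loosely defined. The rule opens with SAEs at least possibly related to treatment, while the cited 21% reference rate is described without attribution. I therefore draw nothing from that rate.
- The table's column for patients on study treatment most naturally means everyone dosed. The replaced-patient question is therefore a minor gap, as is the n = 20 overlap.

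**Conclusion.** The concern holds and must be fixed. The written criterion and the table are different rules at every sample size from 6 to 32. The printed 71% halting and expected sample size of 19 at a true 60% rate follow from neither.

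The boundary comparison rests only on the stated prior, cut-off and limit. The halting percentages also assume a look after every patient from n = 6 and a cap of 32. The finding that 71% cannot come from the table needs less: only that the rule is applied through patient 32. The small gap at 50% may reflect the unstated schedule, and I give it no weight.

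The documents do not establish which rule was intended, and this review does not choose one.

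**What to change.** The sponsor should state which rule is intended and regenerate criterion, table and operating characteristics from one computation. The figures below assume a look after every patient and should be recomputed for the schedule adopted.

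- **If the 80%/30% sentence is kept:** the table it implies is 3 (n = 6–7), 4 (8–9), 5 (10–12), 6 (13–15), 7 (16–18), 8 (19–21), 9 (22–24), 10 (25–27), 11 (28–30), 12 (31–32). Halting is about 20/55/86/98/>99% at true rates of 20–60%, with expected n 27/20/13/9/7. The price is an accrual pause in about 20% of trials at a true 20% rate.
- **If the table is kept:** replace the sentence with the criterion that generated the table, which only the sponsor can supply, and align the opening statement about exceeding 30%. Halting is about 1/7/29/66/92%, with expected n 32/30/26/20/13. The plan must then say openly that the rule halts only about 29% of trials at a true 40% rate.

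In either case, state the look schedule, remove the n = 20 overlap, define the counted event once, and say whether replaced patients who were dosed count. Say also what applies if more than 32 patients are dosed, reconciling sections 5.2, 5.10 and 11.3. The cost is a text and table correction, with no added patients or data.

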| Duration of Administration                   | Patients may continue treatment for 2 years in absence of disease progression or unacceptable toxicity.                                                                                                                                                                                                                                                                                                                                                                                                                                                                                                                                                                                                                                                                                                                                                                                                                                                                                                                                                                                                                                                                                                                                                                                                                                                                                                                                                                                                                                                                                                                                                                                                                                                                                                                                                                            |

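### The toxicity halting rule counts every accrued patient as fully observed, so if SAEs are delayed it halts accrual less often than Section 11.5 states at true SAE rates of 30–50%

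*Combined protocol and SAP*

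**What the plan says.** Section 11.5 of the combined protocol and SAP sets "stopping rules for documented SAE events that are at least possibly attributable to the study regimen". The SAE rate in the reference trial is "defined as the percentage of patients experiencing at least one SAE during study treatment". Accrual is to be halted "if we become confident from accumulating study data that the SAE rate, defined in the same way, involves more than 30% patients". Treatment is long: "Patients may continue treatment for 2 years in absence of disease progression or unacceptable toxicity" (Study Synopsis, repeated in 5.1).

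The denominator has two names. The text says "The following table lists the number of patients accrued and the number of patients experiencing an SAE to trigger stopping the trial", while the table heading reads "Number of patients on study treatment". The start is also tied to accrual: "The rule is implemented after 5 patients are accrued". The threshold is 6 SAEs for 6–10 patients, then rises by one for every two patients, to 17 for 31–32.

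For true SAE rates of 20%, 30%, 40%, 50% and 60%, Section 11.5 states that "the trial would stop early <1%, 8%, 30%, 62%, and 71%, respectively", with expected sample sizes of 32, 31, 27, 21 and 19. It gives no accrual rate and no SAE timing, and does not say how patients still under observation are counted. Sections 5.10 and 7.1.1 make a patient evaluable for toxicity from the first dose.

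**The concern.** A patient dosed yesterday enters the denominator as a non-event, although that patient's SAE may come weeks or months later. Each new enrolment can move the trial into a row that needs one more SAE before earlier patients' outcomes are known. The observed proportion then lags the true rate, and lags more the faster accrual runs.

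This table is the only numerical safety trigger in the plan, for a combination whose two agents, according to Section 5.1, had been evaluated separately. If its stated operating characteristics assume complete observation that the written rule does not provide, the review committee and the IRB have been given a more sensitive rule than the one that will run, and more patients would be enrolled before a halt.

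**Working it through.** **1. Reproduce the printed figures with instant outcomes.** Let r(n) be the printed threshold (11 used at n = 20, which appears in two rows) and f(n, x) the probability of reaching n patients with x SAEs and no earlier crossing. Then

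f(n, x) = (1 − p)·f(n − 1, x) + p·f(n − 1, x − 1).

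At each n from 6 to 32, the mass with x ≥ r(n) is added to the stopping probability and removed.

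| True SAE rate | 20% | 30% | 40% | 50% | 60% |
|---|---|---|---|---|---|
| Printed stopping | <1% | 8% | 30% | 62% | 71% |
| Exact, instant outcomes | 0.8% | 7.4% | 29.4% | 65.6% | 92.1% |
| Printed expected N | 32 | 31 | 27 | 21 | 19 |
| Exact expected N | 31.8 | 30.5 | 26.4 | 19.5 | 13.0 |

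The first three stopping entries agree within a point. The printed figures therefore behave as if each outcome were known at accrual. Using 12 at n = 20 changes little (0.8%, 7.3%, 29.2%, 65.3%, 92.0%).

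**2. Why delay dilutes.** Assume 32 patients over 24 months (32/24 = 1.33 a month) and SAEs uniform over 4 months. About 4 × 1.33 = 5.3 patients are then inside that period at any time, on average half observed, so about 2.7 patients' worth of outcome is missing. At 16 accrued and a true 50% rate, the expected SAE count is 0.5 × (16 − 2.7) = 6.7 instead of 8, against a threshold of 9. With 12-month accrual, 5.3 patients' worth is missing and the expected count is 0.5 × (16 − 5.3) = 5.3.

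**3. Simulate the rule as written.** Assumptions: all accrued patients in the denominator; random arrivals averaging 32 over 12, 18 or 24 months; SAE times uniform over 1, 4 or 6 months from first dose. There were 20,000 trials per cell, except the 12-month, 1-month cell (6,000 trials, arrivals uniform over the period). The outcome is a halt before the last patient enters. Entries are for accrual over 12 / 18 / 24 months.

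| SAEs spread over | True 30% (printed 8%) | True 40% (printed 30%) | True 50% (printed 62%) |
|---|---|---|---|
| 1 month | 5 / 6 / 6% | 22 / 25 / 26% | 57 / 60 / 61% |
| 4 months | 1 / 2 / 3% | 7 / 13 / 16% | 27 / 40 / 47% |
| 6 months | 0.3 / 1 / 2% | 2 / 7 / 11% | 12 / 27 / 37% |

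Allowing for other arrival patterns and simulation error, the ranges at 50% are about 56–62%, 26–49% and 10–39%. At 40% they are about 22–27%, 5–17% and 2–12%. Expected enrolment at 50% with the 4-month spread is 28.6, 26.0 and 24.5 patients, against the printed 21.

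**4. Count triggers after the last entry too.** At 50% with the 4-month spread, total triggering rises to about 47–56%, still below 62%.

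**5. The 60% entry.** The last row alone (17 or more of 32) is reached with probability 83.5%, so 71% is too low before any delay is considered. With 24-month accrual the rule as written still halts in 90%, 81% and 72% of trials for the three SAE spreads.

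**The case against.** A reader might infer that the rule has no observation period at all. That is too strong: the rate is defined over study treatment, and Section 8.1 collects adverse events to 100 days after the last dose. What is missing is a fixed window and a rule for patients only partly through it. The bracketed mention of dose limiting toxicity in Section 12.2 adds little either way.

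A reader might also infer that the rule cannot deliver its printed probabilities at any rate. The 60% entry refutes this: the printed 71% is understated even with complete observation, and the diluted rule can still meet it.

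The best defence concerns size. If most SAEs occur in the first month, the loss is small (57–61% against 62% at a true 50% rate). The documents give no timing, so nothing shows that the larger losses would occur. This stands, and is why the result is a range. Counting only halts before the last entry also widens the gap. That measure is defensible because the stated action is to halt accrual, but the other count should be shown beside it.

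The table heading could mean patients currently on treatment. Patients who leave would then drop out of the denominator, which pushes the other way; that reading was not simulated. Finally, 24-hour SAE reporting (8.4.1) and quarterly DSMC review (13.0) continue whatever the table says, though neither carries an SAE threshold. At a true 30% rate, fewer halts might even be welcome, but they are not what Section 11.5 states.

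**Conclusion.** The concern holds for true SAE rates of 30–50%. The printed stopping probabilities assume outcomes known at accrual, and the written rule provides no follow-up requirement to make that true. Delay lowers the chance of halting in every scenario examined: slightly if SAEs come within a month, and from about a quarter to more than four fifths below the printed value at a true 50% rate if they spread over 4 to 6 months. The size rests on assumed accrual of 12–24 months, assumed uniform SAE timing, and the reading that all accrued patients count.

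The documents do not support the inference that the rule fails at every rate, or that the errors at 50% and 60% in the printed row come from dilution. Those entries differ from the exact values (65.6% and 92.1%) with no delay at all. A separate defect is that the table rows do not follow from the stated uniform prior and 80% criterion, which would give 3 of 6, 5 of 10, 8 of 20 and 12 of 32 in place of 6, 6, 11 (or 12) and 17.

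**What to change.** In Section 11.5:

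- Define a fixed SAE window from first dose, for example the first two 28-day cycles.
- Index the table by patients who have completed that window, on or off treatment, and count SAEs within the window for those same patients. Numerator and denominator then match, and instant-outcome calculations apply to the completed patients.
- Use one denominator term in place of *accrued* and *on study treatment*.
- Restate the stopping probabilities and expected sample sizes with accrual and SAE-timing assumptions, and correct the table rows in the same revision.

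The 30% limit must be set for the chosen window. If SAEs spread evenly over 4 months (about 122 days), a 56-day window captures 56/122 = 46% of them, so a 50% rate over treatment becomes 0.46 × 50% = 23% within the window. On the present rows that lies between the exact 0.8% (at 20%) and 7.4% (at 30%) chances of stopping. The window and the limit therefore have to be chosen together.

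If SAEs are instead to count as soon as they occur, while non-events count only after the window, the section should say so and state the cost. With an 8-week window and the present rows, false halts at a true 30% rate are about 7% if SAEs spread over 4 months but 11–19% if they fall in month 1.

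The cost is a few sentences and a re-run of the calculations, with no extra patients or visits. With matched counting the rule reacts later by up to one window, patients enrolled meanwhile are exposed, and SAEs after the window are left to the quarterly DSMC review.
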